2.3 Primary endpoint

The primary endpoint is the percentage of time spent in glycaemic target range (70-180 mg/dL (3.9-10.0 mmol/L), both inclusive) during the 2-week maintenance period. The FreeStyle Libre Pro device stores four measurements per hour and a subject with complete data will contribute with 14*24*4=1344 measurements from each 2-week period. The analysis will discard data from the first 24 hours as per communication with the vendor and so subjects with complete data will contribute with 13*24*4=1248 glucose recordings. The number of recorded measurements may be smaller for various reasons for subjects in the PP analysis set. Following ADA criteria we will demand that at least 70% of two weeks FGM measurements, corresponding to 10 days of FGM data, must be available for subjects to be included in the analysis. The percentage of time spent in glycaemic target range will be calculated as the number of recorded measurements in glycaemic

| Statistical Analysis Plan | | Date: | 23 January 2020 | Novo Nordisk |
|----------------------------|--------------|----------|-----------------|--------------|
| Trial ID: 1250-4419 | CONFIDENTIAL | Version: | 2.0 | |
| UTN: 1111-1203-0580 | CONFIDENTIAL | Status: | Final | |
| EudraCT no: 2017-004047-20 | | Page: | 8 of 17 | |

target range (70-180 mg/dL (3.9-10.0 mmol/L), both inclusive) divided by the total number of recorded measurements.

The primary estimand will be estimated by the primary endpoint analysed in a linear mixed model with treatment and period as fixed effects, subject as a random effect and with an unstructured residual variance matrix.

Using the unblinded data and before DBL, visual tools will be used to determine whether the data, including the primary endpoint, are normally distributed. If it is then found that the data are not normal, an appropriate transformation will be performed and this will be documented in a SAP or the DBL minutes.

Superiority of IDeg OD compared to IGlar 100U/mL OD with respect to percentage of time spent in glycaemic target range will be considered confirmed if non-inferiority is confirmed and the lower limit of the two-sided 95% confidence interval of the difference (IDeg OD - IGlar 100U/mL OD) is entirely above zero or equivalently if the p-value for the one-sided test of

H0: $D \le 0\%$ against HA: D > 0%

is smaller than 2.5%, where D is the estimated mean difference of time spent in glycaemic target range (IDeg OD - IGlar 100U/mL OD). As such, a fixed hierarchical testing procedure will be applied, which will effectively adjust for multiple testing.

Non-inferiority will be evaluated by comparing the lower limit of the two-sided 95% confidence interval for the difference between IDeg and IGlar 100U/mL to a non-inferiority margin of 0.2h/24h (0.83%). If the lower CI limit is above -0.83%, non-inferiority will be considered established. The two-tailed p-value will be reported for the test of superiority.

Missing data due to intercurrent events such as trial discontinuation is not relevant since the primary estimand is based on the PP analysis set.

A sensitivity analysis will be performed to account for heteroscedasticity due to a varying number of FGM readings within the 70% demand. Specifically, the primary endpoint will be analysed by applying the weight statement in the proc mixed procedure with weights calculated as the square root of the total number of FGM readings.

An additional sensitivity analysis will be performed where all subjects who have FGM readings for at least seven consecutive days will be included. Weighting will be performed as described previously.

Following specifications from the vendor the accuracy of the FGM measurements can be influenced by intake of either ascorbic or/and salicylic acid [1]. The level of consequence depends on the amount of the interfering substance active in the body [1]. Due to the trial design, doses of non-

| Statistical Analysis Plan | | Date: | 23 January 2020 | Novo Nordisk |
|----------------------------|--------------|----------|-----------------|--------------|
| Trial ID: 1250-4419 | CONFIDENTIAL | Version: | 2.0 | |
| UTN: 1111-1203-0580 | CONFIDENTIAL | Status: | Final | |
| EudraCT no: 2017-004047-20 | | Page: | 9 of 17 | |

diabetic concomitant medications are not collected, and it is hereby not possible to identify high risk subjects. A sensitivity analysis will be performed where all FGM measurements, for subjects in the PP analysis set, coinciding with intake of ascorbic and/or salicylic acid, will be excluded. Taking washout periods of both ascorbic and salicylic acid (also applicable for multivitamins including ascorbic acid) into consideration, FGM measurements overlapping the start-to-end dates of intake of either drug + 1 day will be omitted in the analysis. This will result in partial or complete FGM profiles being disregarded. Weighting will be applied as described previously to account for heteroscedasticity due to a varying number of FGM readings

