5.2 Subject and trial completion

Approximately 674 subjects will be screened to achieve 472 subjects randomly assigned to trial product.

Approximately 502 subjects are planned to be included in the run-in period.

Trial period completion for a subject:

Trial period completion is defined as when the randomised subject has completed the final scheduled visit ('end of trial' according to the flowchart).

'Date of trial completion' is the date the subject completed the final scheduled visit.

Treatment period completion for a subject:

Treatment period completion is defined as when the randomised subject has received the required treatment, and attended the 'end of treatment' visit according to the flowchart.

The treatment period 1 starts at Visit 3 and is defined as when the randomised subject has received the required treatment for at least 18 weeks and attended Visit 21 according to the flowchart.

The treatment period 2 starts at Visit 21 and is defined as when the randomised subject has received the required treatment for at least 18 weeks and attended Visit 39 according to the flowchart.

Required treatment:

Completion of both treatment periods is required for contribution to the analysis. Only the data from subjects completing 16 weeks of titration and 2 weeks of maintenance wearing the FreeStyle Libre Pro device, with both trial products, will be used in the outcome analyses.

Protocol
Trial ID: NN1250-4419

CONFIDENTIAL
Date: 01 June 2018 Version: 3.0
Status: Final Page: 18 of 68

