2.4 Secondary endpoints

Supportive secondary endpoints

Percentage of time spent in tight glycaemic target range (70-140 mg/dL (3.9-7.8 mmol/L), both inclusive is calculated in the same way as the primary endpoint using the relevant ranges. A sensitivity analysis using weights to account for heteroscedasticity due to a varying number of FGM readings will be performed as described previously.

Percentage of time spent in nocturnal glycaemic target range 70-140 mg/dL (3.9-7.8 mmol/L) both inclusive, in the nocturnal period (00:01 am–05:59 am both inclusive) will be calculated in the same way as the primary endpoint but only using readings with a time stamp in the relevant time period. A sensitivity analysis using weights to account for heteroscedasticity due to a varying number of FGM readings will be performed. As described previously the weights are calculated based on the total number of FGM readings and will in so doing not be adjusted to account for the lower number of nocturnal readings.

All the supportive secondary endpoints regarding time spent in target range are analysed and tested in the same model as the primary endpoint, i.e. one sided tests of the mean difference favouring IDeg must be statistically significantly different from zero at the 0.025 level to support superiority.

As stated in Section 9.1.1.4 of the protocol, sites are instructed not to initiate FGM monitoring periods that will contain daylight saving clock shifts. During data analysis it will be checked if this rule is obeyed, and the length of both the entire day in question in general, and the nocturnal period in question in particular will be adjusted equivalently when it is not. For example, if a subject is under FGM monitoring in the US on 11-MAR-2018 the nocturnal period will start at 00:01AM and end at 04:59 (nominal sensor time) instead of 05:59. In the data analysis one hour will be added to the recorded time points from 02:00 and onwards. In practise then, 11-MAR-2018 will consist of no more than 23h of FGM readings, and the nocturnal period of no more than 4h and 58 minutes of FGM readings. If on the other hand a subject is under FGM monitoring on 04-NOV-2018 in the US one hour will be deducted from the time recorded time points. This will then consist of no more than 25 hours of FGM readings, and the nocturnal period of no more than 6h and 58 minutes of FGM readings. The hour between 01:00-02:00 on 04-NOV will be represented twice in the data,

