2.5 Exploratory endpoints

Glycaemic variability will be calculated as the standard deviation (mmol/L) and coefficient of variation (%) of the FGM glucose levels during the 2-week maintenance treatment periods. Both will be analysed and tested with models and tests equivalent to the primary endpoint.

Mean insulin dose in international units is calculated as the mean dose over the maintenance treatment periods for each subject. It will be analysed and tested using models and tests equivalent to the primary endpoint.

Percentage of time spent in the hypoglycaemic alert range (54-69 mg/dL (3.0-3.8 mmol/l), both inclusive) and percentage of time spent in the clinically significant hypoglycaemic range (<54 mg/dL (<3.0 mmol/L)) are calculated in the same way as the primary endpoint using the relevant ranges. A sensitivity analysis using weights to account for heteroscedasticity due to a varying number of FGM readings will be performed as described previously.

All the exploratory endpoints regarding time in range are analysed and tested in the same model as the primary endpoint, i.e. one sided tests of the mean difference favouring IDeg must be statistically significantly different from zero at the 0.025 level to support superiority.

Number of hypoglycaemic episodes <54 mg/dL (<3.0 mmol/L) for at least 15 minutes and number of hypoglycaemic episodes <54 mg/dL (<3.0 mmol/L) for at least 15 minutes in the nocturnal period (00:01-05:59 AM, both inclusive) will be counted as follows: At least two consecutive FGM glucose readings (i.e., readings that follow each other continuously in time) in the specified range are counted as a hypoglycaemic episode. Two hypoglycaemic episodes must be separated by at least 15 minutes above the hypoglycaemic range, equivalent to 2 consecutive FGM readings above the relevant hypoglycaemic range to be counted as two or more episodes instead of one. For the

| Statistical Analysis Plan | | Date: | 23 January 2020 | Novo Nordisk |
|----------------------------|--------------|----------|-----------------|--------------|
| Trial ID: 1250-4419 | CONFIDENTIAL | Version: | 2.0 | |
| UTN: 1111-1203-0580 | CONFIDENTIAL | Status: | Final | |
| EudraCT no: 2017-004047-20 | | Page: | 11 of 17 | |

nocturnal episodes, only FGM readings in the relevant period will be used. Person years of exposure (PYE) will be calculated as

PYE=(N FGM*15 minutes)/(365.25 days/year*(24 hours)/day*(60 minutes)/hour)

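### Does the redundant covariance parameter in the primary mixed model need to be removed from the SAP?

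*SAP*

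**What the plan says.** SAP 2.3 and Protocol 10.3.1 give the same primary model: a linear mixed model "with treatment and period as fixed effects", "subject as a random effect and with an unstructured residual variance matrix". Protocol 5.2 fixes the data structure: "Completion of both treatment periods is required for contribution to the analysis". Each subject in the primary analysis therefore supplies two values, one per maintenance period.

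SAP 2.3 adds three weighted sensitivity analyses of the primary endpoint:

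- The first is fitted by "applying the weight statement in the proc mixed procedure", with weights equal to the square root of the number of readings.
- The second widens entry to subjects whose readings for "at least seven consecutive days will be included".
- The third removes readings taken during ascorbic or salicylic acid use, and the SAP notes: "This will result in partial or complete FGM profiles being disregarded".

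The model is reused for the supportive time-in-range endpoints, tested "in the same model as the primary endpoint" (SAP 2.4), and for the exploratory time-in-range endpoints (SAP 2.5). SAP section 3, which lists changes from the protocol, leaves the covariance structure as it was. Neither document says which term is kept if the software cannot estimate both.

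**The concern.** A random subject effect contributes one variance, and an unstructured 2×2 residual matrix contributes two variances and a covariance. That makes four parameters for a marginal covariance with three elements. Taken literally, the likelihood has a flat direction. The programmer may meet a singular-Hessian or convergence message and have to decide what to drop, and the SAP does not record that decision.

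If the decision moved the primary estimate or its standard error, an open choice would sit under both the superiority and the non-inferiority tests. There is also a less obvious issue. The WEIGHT statement acts on the residual matrix and not on the random effect. Two forms that are interchangeable without weights then become different models, and the SAP does not say which one the weighted runs use.

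**Working it through.** **Inputs from the documents.** Planning effect 0.39 h and SD of the within-pair difference 2.6 h, 85% power, 401 pairs (SAP 2.1). Readings per period from 960 (SAP 2.2) to 13×24×4 = 1248 (SAP 2.3). Non-inferiority margin 0.83 points (SAP 2.3). On the percentage scale, the SD is 2.6/24 = 10.83 points and the effect is 0.39/24 = 1.625 points.

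**Assumed, not in the documents.** Subject variance 191 and residual variance 58.7 per period. These give a difference SD of √(2×58.7) ≈ 10.83 and a between-period correlation of 191/249.7 = 0.765. The spread of reading counts, and the share of residual variance that shrinks with the number of readings, are also assumed.

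**1. The plan's own figure.** The exact paired t-test at two-sided 5% gives 401 pairs (power 0.850), and all six cells of the sample-size table reproduce. 401/0.85 rounds up to 472. The calculation uses only the SD of the difference, so the form of the covariance does not enter.

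**2. Redundancy without weights.** Write V = s·J + R, where s is the subject variance, J the 2×2 matrix of ones and R the residual matrix. Replace s by s + c and R by R − c·J. V does not change. The fixed-effect estimate, its standard error and the REML criterion depend on the covariance only through V, so they do not change either. In one simulated data set, moving s from 0 to 124 with R adjusted to match left −2 REML at 2370.454, the estimate at 1.2826 and the standard error at 0.5466. The smallest Hessian eigenvalue was 3×10⁻¹⁰, which is the flat direction.

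**3. The two three-parameter forms.**
- Form (i): random subject effect with period-specific residual variances. It needs s = V₁₂ and residual variances V₁₁ − V₁₂ and V₂₂ − V₁₂.
- Form (ii): unstructured R with no random effect, so R = V.

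They are the same model when 0 ≤ V₁₂ ≤ min(V₁₁, V₂₂). In simulated trials inside that range, estimates and standard errors agreed to numerical precision.

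**4. With weights.** Here Vᵢ = s·J + Wᵢ^(−1/2) R Wᵢ^(−1/2), with w = √(n/1248). Dividing by 1248 only rescales R. For a period at the minimum count, w = √(960/1248) = 0.877 and 1/w = 1.140. Form (i) gives that period a variance of 191 + 58.7×1.140 = 257.9. Form (ii) gives 249.7×1.140 = 284.7, because it also inflates the between-subject part. The forms do differ, but the effect on the treatment difference is small. The table shows 1,000 simulated trials per setting.

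| Weighted run | Gap in estimate, points: median / 95th percentile / maximum |
|---|---|
| 70% rule, 960–1248 readings | 0.012 / 0.03 / 0.07 |
| Seven-day run, 25% of subjects with one period at 672–1248 | 0.018 / 0.05 / 0.08 |
| Acid run, 10% of subjects with one period cut to 1–7 days | 0.03 / 0.09 / 0.17 |
| Acid run, 25% of subjects | 0.06 / 0.16 / 0.26 |
| Acid run, 50% of subjects | 0.08 / 0.22–0.24 / 0.42 |

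Standard errors were 0.54 to 0.68, and interval coverage was 94–96% for both forms. Against the planning standard error of 10.83/√401 = 0.54, the median gap in the first row is 0.012/0.54, or about 2%.

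**5. The model exactly as written, with weights.** The shift in step 2 now changes Vᵢ, so the four parameters are no longer exactly redundant, only almost so (smallest eigenvalue 6×10⁻⁶). Fitted literally, the model was a median 0.002 to 0.044 points from form (i).

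**The case for a change.** The best argument for a change is cost. One line naming a form would make the model identifiable as written and would remove a programmer's choice. Three further points support it.

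First, the unweighted equivalence is conditional. If the between-period covariance is negative, or exceeds the smaller period variance, form (i) hits a boundary. At correlation 0.9 and variance ratio 1.5, estimates differed by up to about 0.1 points and standard errors by up to about 12%. This is unlikely for the primary endpoint but possible for the skewed hypoglycaemia-range endpoints that reuse the model. The condition stands. It limits form (i), though, not the plan: the written model contains an unstructured residual matrix and can represent any covariance. The obvious response to a singularity message, dropping the random effect, loses nothing.

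Second, the SAP does not say whether the matrix is indexed by period or by treatment. In small unweighted simulations the two indexings differed by up to 0.11 points with equal variances and 0.16 at a period-variance ratio of 1.3. This is a real omission, but a separate one, and naming one of the two forms would not settle it. Ordering repeated values by period is the natural reading in a cross-over.

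Third, the acid run could show a visible gap. The largest figures need half the subjects to have exactly one period cut to a few days. SAP 2.3 deletes by start and end dates of intake, so continuous use would remove both profiles and leave no contrast in weights. Wholly missing single profiles were not simulated.

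**Conclusion.** The parameter count is correct and the wording is untidy, but no change to the plan follows. Without weights, the redundancy cannot affect the primary estimate, standard error, interval, superiority or non-inferiority decision, or sample size. That is algebra and needs no assumption. What remains is an unrecorded detail in sensitivity runs that carry no decision rule. The median gap is about 0.01 to 0.02 points under the 70% rule and in the seven-day run, and 0.03 to 0.08 points in the acid run under the assumed truncation, against a standard error of about 0.55. Both forms have close to nominal coverage, so either choice is valid.

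The weighted figures rest on assumed variances and reading counts, and on the WEIGHT statement scaling the residual matrix only. They come from independent REML code, as PROC MIXED itself was not run. Substituting an equal-variance residual would not be a neutral tidy-up: it removes a further parameter and moved the unweighted estimate by up to 0.16 points at a period-variance ratio of 1.3.

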4.1 Primary, secondary and exploratory objective(s)

The primary objective is to compare the effect on glycaemic control of IDeg versus IGlar 100U/mL in a population of T2DM subjects with or without OADs, using FGM.

Estimand:

The primary estimand is the treatment difference between IDeg and IGlar 100U/mL with respect to percent time spent in glycaemic target range for all randomised subjects that can use the FGM sensor and adhere to at least 18 weeks of treatment on both insulins. An intercurrent event for the primary estimand include lack of effect from any of the insulins leading to a need for initiation of other diabetes medication(s). As described in section 8.1 in the protocol, treatment intensification may result in trial discontinuation. The primary estimand will handle these intercurrent events as withdrawals and only use data from completers. The primary estimand is the principle stratum direct effect for the population of completers.

Protocol Trial ID: NN1250-4419	CONFIDENTIAL	Date: Version: Status:	01 June 2018 3.0 Final	Novo Nordisk
		Page:	15 of 68	

The population level summary statistics is the average percent of time spent in glycaemic target during maintenance for completers. For comparing the two treatments the relevant summary is the difference in the means.

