10.3.1 Primary endpoint

The primary endpoint is the percentage of time spent in glycaemic target range (70-180 mg/dL (3.9-10.0 mmol/L), both inclusive) during the 2-week maintenance period. The FreeStyle Libre Pro device stores four measurements per hour and a subject with complete data will contribute with 14*24*4=1344 measurements from each 2-week period. The analysis will discard data from the

Protocol Trial ID: NN1250-4419	CONFIDENTIAL	Date: Version: Status:	01 June 2018 3.0 Final	Novo Nordisk
		Page:	39 of 68	

first 24 hours as per communication with the vendor and so subjects with complete data will contribute with 13*24*4=1248 glucose recordings. The number of recorded measurements may be smaller for various reasons for subjects in the PP analysis set. Following ADA criteria we will demand that at least 70% of two weeks FGM measurements, corresponding to 10 days of FGM data, must be available for subjects to be included in the analysis. The percentage of time spent in glycaemic target range will be calculated as the number of recorded measurements in glycaemic target range (70-180 mg/dL (3.9-10.0 mmol/L), both inclusive) divided by the total number of recorded measurements.

The primary estimand will be estimated by the primary endpoint analysed in a linear mixed model with treatment and period as fixed effects, subject as a random effect and with an unstructured residual variance matrix.

Using the unblinded data and before DBL, visual tools will be used to determine whether the data, including the primary endpoint, are normally distributed. If it is then found that the data are not normal, an appropriate transformation will be performed and this will be documented in a SAP or the DBL minutes.

Superiority of IDeg OD compared to IGlar 100U/mL OD with respect to percentage of time spent in glycaemic target range will be considered confirmed if non-inferiority is confirmed and the lower limit of the two-sided 95% confidence interval of the difference (IDeg OD - IGlar 100U/mL OD) is entirely above zero or equivalently if the p-value for the one-sided test of

H0: $D \le 0\%$ against HA: D > 0%

is smaller than 2.5%, where D is the estimated mean difference of time spent in glycaemic target range (IDeg OD - IGlar 100U/mL OD). As such, a fixed hierarchical testing procedure will be applied, which will effectively adjust for multiple testing.

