2.1 Sample size determination

The sample size calculation is based on the primary objective for the primary estimand and the primary endpoint of the trial, and is performed as a paired-sample calculation in terms of the mean and standard deviation of the within pair difference within the PP using the paired t-test. Only one previous Novo Nordisk trial using CGM has had a similar design: NN1250-3874 comparing IDeg and IGlar 100U/mL in 24 T1DM subjects using a cross-over design. Regarding time in glycaemic target range (70-180 mg/dL) during the full 24 hours of the day, the within pair difference between IDeg and IGlar 100U/mL had a mean of 0.39 hours and a standard deviation of 2.3. Two previous Novo Nordisk studies have used CGM in T2DM subjects in parallel arm designs, NN1250-3579 and NN1250-3668. However, CGM technology used in those two T2DM trials is outdated compared to the devices used in the current trial, and they are therefore deemed irrelevant as to

| Statistical Analysis Plan | | Date: | 23 January 2020 | Novo Nordisk |
|----------------------------|--------------|----------|-----------------|--------------|
| Trial ID: 1250-4419 | CONFIDENTIAL | Version: | 2.0 | |
| UTN: 1111-1203-0580 | CONFIDENTIAL | Status: | Final | |
| EudraCT no: 2017-004047-20 | | Page: | 7 of 17 | |

guidance on expected difference between the two treatments in this trial. The results from the NN1250-3874 trial are used for sample size calculation despite the differences from the present trial, i.e. indication and length of maintenance treatment. A conservative standard deviation of 2.6 is used. To detect a mean difference of 0.39 with 85% power with a standard deviation of 2.6 based on a paired t-test and 1:1 randomisation requires 401 subjects included in the PP. See Table 3 for sample sizes based on a range of standard deviation and for mean differences of 0.39 and 0.5

| Effect | | | | |
|--------|------|------|--|--|
| SD | 0.39 | 0.50 | | |
| 2.0 | 239 | 146 | | |
| 2.3 | 315 | 192 | | |
| 2.6 | 401 | 245 | | |

Sample size is computed for 1:1 randomisation and 85% power. SD: standard deviation. respectively.

Table 1 Sample size and power for various standard deviations and effects

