where N_FGM is the total number FGM readings in the relevant period. The number of hypoglycaemic episodes will be analysed using a negative binomial regression with treatment and period as fixed effects, subject as a normally distributed random effect and the log(PYE) as an offset. A p-value smaller than 0.025 for the one sided test of the rate ratio in favour of IDeg will be considered as support for superiority of IDeg over IGlar 100U/mL. If this model does not converge, a Poisson regression model will be fitted.

CONFIDENTIAL

Date: Version: Status: Page:

23 January 2020 2.0 Final 12 of 17 Novo Nordisk

3 Changes to the statistical analyses planned in the protocol

Updates to section 10 in protocol version 3.0 is described below.

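### The primary endpoint may be transformed after a visual check of unblinded data, yet the estimand, the hypotheses and the -0.83-point margin exist only on the raw percentage scale

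*SAP*

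**What the plan says.** By default, Protocol 10.3.1 and SAP 2.3 analyse the percentage of time in range untransformed, in a linear mixed model with treatment and period as fixed effects and subject as a random effect. Both then add a conditional step. In the SAP: "Using the unblinded data and before DBL, visual tools will be used to determine whether the data, including the primary endpoint, are normally distributed". If the answer is no, "an appropriate transformation will be performed and this will be documented in a SAP or the DBL minutes". The protocol has the same rule: "If it is then found that the data are not normal, an appropriate transformation will be performed".

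Every confirmatory quantity is set on the raw scale:

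- **Estimand** (Protocol 4.1): "For comparing the two treatments the relevant summary is the difference in the means".
- **Hypotheses** (SAP 2.3): H0 and HA are stated in percent, "where D is the estimated mean difference of time spent in glycaemic target" range, IDeg minus IGlar.
- **Margin** (SAP 2.3): 0.2 h per 24 h, or 0.83 percentage points (pp). "If the lower CI limit is above -0.83%, non-inferiority will be considered established".
- **Sample size** (SAP 2.1): it "is performed as a paired-sample calculation in terms of the mean and standard deviation of the within pair difference", in hours per day.

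SAP section 3 opens with "Updates to section 10 in protocol version 3.0 is described below" and lists twelve changes, 3.1 to 3.12. None of them concerns the transformation clause, so it stands unchanged in SAP version 2.0.

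**The concern.** The clause names the primary endpoint explicitly. It gives no threshold for non-normality, no candidate transformations, no margin for a transformed scale and no rule for returning to percentages. It also does not say that the raw-scale result remains decisive.

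Three consequences follow if a non-linear transformation is used:

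1. If superiority fails, non-inferiority is the only positive claim left, and it has no defined margin.
2. Superiority is tested on a mean of transformed values, which is not the stated difference in mean percentages.
3. The 2.5% one-sided error is not guaranteed if the treatment codes can inform the choice of scale. The trial is open-label, so the word unblinded may only describe the data, but nothing in the plan keeps that choice apart from treatment-coded results.

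The superiority claim is not blocked by the undefined margin. A lower limit above zero exceeds any negative margin on any monotone increasing scale.

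**Working it through.** **Inputs from the documents.** Effect 0.39 h, SD of the within-subject difference 2.6 h, power 85%, 401 completers, margin 0.2 h (SAP 2.1 and 2.3), and 15% non-completion (Protocol 10.1).

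**Step 1: the plan's own figure.** The paired t-test with the non-central t distribution and two-sided 5% gives n = 401 (power 0.8500). All six cells of the sample-size table reproduce. 401/0.85 = 472 and 0.2/24 = 0.83%. The sample size is therefore tied to the raw scale.

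**Step 2: how often non-inferiority is the only positive claim.** The standard error is 2.6/√401 = 0.130 h, and 0.130/24 = 0.54 pp. With 400 df and non-centrality D/SE for superiority or (D + 0.2)/SE for non-inferiority:

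| True D (h) | Superiority | Non-inferiority | Non-inferiority only |
|---|---|---|---|
| 0 | 2.5% | 33.6% | 31% |
| 0.1 | 11.7% | 63.5% | 52% |
| 0.2 | 33.6% | 86.7% | 53% |
| 0.39 | 85.0% | 99.5% | 14% |

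The last column is the difference of the unrounded values.

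**Step 3: the margin on a transformed scale.** On the logit scale the margin is logit(p - 0.2/24) - logit(p), which depends on the reference mean p. The documents give no planning mean, so p is assumed:

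| Assumed p | 60% | 70% | 80% | 90% |
|---|---|---|---|---|
| Logit margin | -0.035 | -0.039 | -0.051 | -0.089 |

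**Step 4: effect on the non-inferiority verdict.** 40,000 null 2×2 crossover trials (200 + 201 completers) were simulated in each of two assumed logit-normal settings: mean 69% with skewness -0.7, and mean 80% with skewness -1.3. Within-subject spread was calibrated so that the SD of the difference is 10.8 pp (2.6 h). Treatment was tested by the sequence contrast. With D = 0, non-inferiority is met in 34% of trials on the raw scale. On logits:

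| Setting | Margin set at | Non-inferiority met |
|---|---|---|
| Mean 69% | 60 / 70 / 80% | 23 / 29 / 44% |
| Mean 80% | 70 / 80 / 90% | 20 / 30 / 70% |

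Even with the margin set nearest the true mean, the logit and raw verdicts differ in 10% and 13% of trials.

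**Step 5: type I error for superiority, same simulations.**

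| Choice of scale | Mean 69% | Mean 80% |
|---|---|---|
| Raw | 2.5% | 2.6% |
| Logit | 2.5% | 2.7% |
| Arcsine | 2.5% | 2.6% |
| Better of raw and logit | 3.2% | 3.8% |
| Best of all three | 3.2% | 3.8% |

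Raw and logit superiority conclusions disagree in 1.4% and 2.2% of trials.

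**Step 6: whether a transformed test still tests D.** Illustrative paired beta data were used: n = 401, 4,000 runs, IGlar mean 72%, correlation 0.8, SD of the difference about 2.5 h. These inputs are assumptions.

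| Scenario | Raw | Logit | Arcsine |
|---|---|---|---|
| Equal means; between-subject SD 17 (IDeg) vs 15 pp (IGlar): rejection rate | 2.4% | 43.6% | 11.9% |
| True benefit 0.39 h; SD 15 (IDeg) vs 17 pp (IGlar): power | 88% | 38% | 73% |

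When the two treatments have the same mean but different spread, the transformed means differ, and the transformed test rejects although D = 0. The raw test holds its level on these skewed data.

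**The case against.** The strongest reply is that the written trigger is the shape of the distribution, not the treatment result. That is correct. A simulation of such a rule used 20,000 null trials per setting and switched to logit when the skewness, inspected by treatment, crossed a threshold. It gave one-sided error of 2.7% and 2.8%, against 2.6% and 2.8% for raw alone. Seeing the codes while judging shape did not by itself inflate the error. The 3.2 and 3.8% figures need a choice steered by the result. The documents do not describe such a choice, though they do not prevent it.

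The harm is also conditional. The data must be judged non-normal and a non-linear transformation chosen; for the non-inferiority claim, superiority must fail as well. The 31/52/53/14% figures show how often non-inferiority would be the only positive claim. They are not the probability that this problem arises, which cannot be computed because the chance of a transformation is unknown. The widest spreads in step 4 come from margins set about 10 points from the true mean. The 10% and 13% disagreements are the fairer measure.

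Finally, D and the margin are stated in percent, so a reader might infer that any transformed analysis must report back on that scale. No rule for doing so is given, and the mean of transformed values does not determine the difference in raw means. These points limit the size of the concern but do not remove it.

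**Conclusion.** The concern holds and should be fixed. If the clause is followed with a non-linear transformation, stand-alone non-inferiority has no defined margin, and superiority is assessed on a quantity other than the stated estimand. This affects the trial's only confirmatory endpoint, since Protocol 4.2.2.1 lists no confirmatory secondary endpoints.

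The result in step 2 rests only on the plan's 401 completers, SD of 2.6 h and 0.2 h margin. The logit margins and all simulated rates rest on assumed means and distributions, because the documents give none. The type I error inflation is a modest worst case and is absent when the scale is chosen independently of treatment. The documents do not show whether a transformation was used.

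**What to change.** Exempt the primary endpoint from the transformation clause. State in SAP 2.3 that non-inferiority and superiority are both tested on the untransformed percentage of time in range, and list this in SAP section 3 as a change to Protocol 10.3.1. With about 401 within-subject differences the raw-scale test does not need normal data: it held about 2.5% in every skewed setting above.

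For the other endpoints, carry out any normality check with treatment and sequence codes masked, and name the fallback in advance. A pre-specified rank or permutation analysis of superiority, or a named transformed analysis, can be kept as a sensitivity analysis.

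The cost is SAP wording only. The estimand, the margin, the 401 completers and the 472 randomised are unchanged.
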